9.3.8 Fertilization Rate

For subjects with >0 oocytes retrieved, the rate of fertilized oocytes to oocytes retrieved will be presented by descriptive statistics by treatment group. Furthermore, for subjects with >0 metaphase II oocytes, the rate of fertilized oocytes to metaphase II oocytes will be presented by descriptive statistics by treatment group. Fertilization rates will be summarized based on the subset of the mITT analysis set.

9.3.9 Number and Quality of Blastocysts on Day 5

The embryos on Day 5 after oocyte retrieval will be summarized on both the embryo level and on the subject level.

Embryo Level

At the embryo level all embryos evaluated will be included in the tables when reporting embryo stage, destiny, and grading. Frequency tables will be produced for the embryo stage, destiny at day 5, blastocyst expansion and hatching status, blastocyst inner cell mass grading, and trophectoderm grading.

Subject Level

At the subject level the following variables will be derived for all subjects in the analysis set. For any subject that did not have a blastocyst, did not have oocyte retrieval, or otherwise had a missing subject-level endpoint, a value of 'NO' or 0 will be imputed, as appropriate.

- At least one blastocyst available
- At least one good-quality blastocyst available
- Number of blastocysts
- Number of good quality blastocysts
- Number of blastocysts transferred

Among the above variables, the number of blastocysts and the number of good quality blastocysts will be analyzed as described in Section 9.1.2 for the primary endpoint. The dichotomous variables of having at least one blastocyst available and of having at least one good quality blastocyst available will be analyzed as described in Section 9.1.2 for secondary pregnancy endpoints. No analysis will be performed for the remaining variables in this section.

At the subject level the following variables will be derived for mITT analysis set subjects that had oocytes retrieved:

• Rate of blastocysts to oocytes retrieved

• Rate of good-quality blastocysts to oocytes retrieved

At the subject level the following variables will be derived for mITT analysis set subjects that had at least one fertilized oocyte:

- Rate of blastocysts to fertilized oocytes
- Rate of good quality blastocysts to fertilized oocytes

10 Safety

10.1 General Considerations

Safety summaries, unless otherwise stated, will be performed using the Safety analysis set and will be summarized as described in Section 1.2.1. Summaries will be made using all subjects, subjects in the <35 years age strata, and subject in the ≥35 years age strata.

All individual subject data will be listed per subject and treatment as observed including any derived values. Adverse event listings will also include an indicator of whether the adverse event occurred before, during, or after the COVID-19 pandemic trial hold.

10.1.1 Imputation rules

Missing values will be treated as missing, except for causality, intensity, seriousness, and outcome of adverse events. A worst-case approach will be used: if causality is missing, the adverse event will be regarded as related to the IMP; if the intensity of an adverse event is missing, the adverse event will be regarded as severe; if seriousness is missing, the adverse event will be regarded as serious; if outcome is missing, and no date of outcome is present, the outcome is regarded as 'ongoing'.

10.2 Safety endpoints

10.2.1 Adverse Events

Adverse events will be coded using MedDRA. Adverse events will be grouped according to the start of both NIMP and IMP as follows:

- Pre-NIMP adverse event, i.e. any adverse event occurring after signed informed consent and before start of NIMP, or a pre-existing medical condition that worsens in intensity after signed informed consent but before start of NIMP.
- Pre-treatment adverse event, i.e. any adverse event occurring after the start of NIMP and before start of IMP, or a pre-existing medical condition that worsens in intensity after start of NIMP but before start of IMP.
- Treatment-emergent adverse event, i.e. any adverse event occurring after start of IMP and before the end-of-trial, or a pre-existing medical condition that worsens in intensity after start of IMP and before end-of-trial.

Treatment-emergent adverse events will be presented in summary tables and listings. Pre-NIMP and pre-treatment adverse events will be presented in a listing only.

Written narratives will be issued for all SAEs and adverse events leading to discontinuation. Adverse events judged by the investigator as being reasonably possibly related to IMP will be termed adverse drug reactions.

Ferring Pharmaceuticals

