6.4.2 First Post-dosing Anti-MENOPUR Antibody Assessment (7-10 Days after Last IMP Dose)

Subjects who have been exposed to MENOPUR liquid or MENOPUR powder must have the first post-dosing anti-MENOPUR antibody assessment performed 7-10 days after the last MENOPUR liquid or MENOPUR powder dose. This may coincide with the transfer visit (section 6.4.1).

For subjects who do not attend the transfer visit, a separate visit must be scheduled, at which the following must take place:

- Blood collection for central laboratory analysis of anti-MENOPUR antibodies
- Recording of use of any concomitant medication
- Recording of adverse events

Date: 14 Oct 2019 E-Study Protocol-21539; Ver. 6.0 Supersedes: 5.0 Page 55 of 103

6.5 βhCG Test

6.5.1 βhCG Test

Subjects who have undergone transfer must attend a visit 10-14 days after transfer.

The following must take place:

- Blood collection for local laboratory analysis of βhCG
- Blood collection for central laboratory analysis of anti-MENOPUR antibodies (second post-dosing assessment (section 6.5.2))
- Dispensing of progesterone, if applicable
- Recording of use of any concomitant medication
- Recording of adverse events

The blood sample for β hCG will be analyzed by the local laboratory and evaluated according to the local reference ranges. In case of doubtful / inconclusive β hCG result, a second test will be performed, preferably within 2 days. Subjects with a positive β hCG test must attend a clinical pregnancy visit 5-6 weeks after transfer (section 6.6). Subjects with a negative β hCG test must proceed to the end-of-trial assessments (section 6.8).

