6.6 Clinical Pregnancy

Subjects with a positive βhCG test must attend a visit 5-6 weeks after transfer.

Date: 14 Oct 2019 E-Study Protocol-21539; Ver. 6.0 Supersedes: 5.0 Page 56 of 103

The following must take place:

- Transvaginal ultrasound of uterus to assess any clinical pregnancy
- Dispensing of progesterone for luteal phase support if a vital pregnancy is confirmed
- Recording of use of any concomitant medication
- Recording of adverse events

If at least one intrauterine gestational sac with fetal heart beat is observed, vital pregnancy is confirmed. For subjects with a vital pregnancy, the next visit is the ongoing pregnancy visit (section 6.7). Subjects with no vital pregnancy must undergo end-of-trial assessments (section 6.8).

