6.7 Ongoing Pregnancy

If a vital pregnancy has been documented, the subject must attend a visit 8-9 weeks after transfer.

The following procedures / assessments must take place:

- Ultrasound (transvaginal or abdominal) of uterus to assess any intrauterine viable fetus
- Recording of use of any concomitant medication
- Recording of adverse events

If at least one intrauterine viable fetus is identified, this confirms an ongoing pregnancy.

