6.8 End-of-trial

If a subject attends the scheduled trial visits, the end-of-trial assessments should take place at the last scheduled trial visit.

Due to the timing of the mandatory anti-MENOPUR antibody assessments, the end-of-trial assessments can at the earliest be performed 21-28 days after the last MENOPUR liquid or MENOPUR powder dose. This may coincide with the β hCG visit for subjects with a negative β hCG test.

The following end-of-trial procedures / assessments must take place, irrespective of whether the subject discontinues the trial prematurely or completes it:

- Blood collection for central laboratory analysis of:
 - Clinical chemistry and hematology parameters
 - Endocrine parameters (AMH)

Trial Code: 000303

Date: 14 Oct 2019
E-Study Protocol-21539; Ver. 6.0
Supersedes: 5.0
Page 57 of 103

- anti-MENOPUR antibodies (second post-dosing assessment) [note: only applicable for subjects who have not already had a blood sample taken for the second post-dosing anti-MENOPUR antibodies assessment as described in section 6.5.2]
- Vital signs
- Physical examination (including weight)
- Gynecological examination
- Drug accountability, if applicable
- Recording of use of any concomitant medication
- Recording of adverse events
- End-of-trial form (completion of trial or premature discontinuation, date and reason for discontinuation, if applicable)

These assessments serve to document the subject's physical health at the end of the trial.

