7.2.13 Adverse Events

Adverse events will be recorded from the time of signed informed consent for participation in the trial until the end-of-trial visit. For each adverse event the following parameters are recorded by the investigator on the Adverse Event Log: description of event, date and time of onset, intensity, causal relation to IMP, action taken to IMP, other actions taken, seriousness of the adverse event, date and time of outcome, and outcome. Definitions of adverse events are provided in section 8.

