10.2.1.2 Incidence of Adverse Events

Treatment-emergent adverse events in each treatment group will be tabulated by system organ class (SOC) and preferred term (PT). The following will be presented: number of subjects reporting an adverse event, the percentage of subjects (%) with an adverse event, and the number of events (E) reported. AEs will be presented by SOC sorted alphabetically and PT sorted in decreasing frequency of occurrence.

Summary tables will be prepared for:

- All treatment-emergent adverse events.
- Treatment-emergent adverse events occurring in ≥2% and ≥5% of subjects in any treatment group.
- Treatment-emergent adverse drug reactions occurring in ≥2% and ≥5% of subjects in any treatment group.
- Treatment-emergent adverse events by causality.
- Treatment-emergent adverse events by intensity.
- Treatment-emergent adverse drug reactions by intensity.
- Treatment-emergent adverse events leading to discontinuation.

- Treatment-emergent serious adverse events.
- Treatment-emergent adverse events leading to death.

Supporting data listings will be provided for:

- All pre-NIMP adverse events sorted by SOC and PT.
- All pre-treatment adverse events sorted by SOC and PT.
- All treatment-emergent adverse events sorted by SOC and PT.
- All treatment-emergent adverse events sorted by center and subject number.
- All unique verbatim and coded terms.
- All SAEs.
- All non-Serious adverse events.
- All adverse events leading to discontinuation.
- All adverse events leading to death.

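### Treatment-emergent adverse events are counted up to a visit whose date depends on pregnancy, so crude adverse event percentages depend partly on the pregnancy rate and no table uses a common window

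*SAP*

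**What the plan says.** SAP 10.2.1 defines a treatment-emergent event as "any adverse event occurring after start of IMP and before the end-of-trial", together with pre-existing conditions that worsen in that period. The tables in SAP 10.2.1.1 and 10.2.1.2 give, for each arm, the "number of subjects reporting an adverse event, the percentage of subjects (%) with an adverse event, and the number of events (E) reported". Protocol 9.8.1 takes every subject in the arm's safety set as the denominator. Neither document plans person-time rates, a fixed risk window, or adverse event tables by pregnancy status.

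Collection stops at the same variable point: "Adverse events will be recorded from the time of signed informed consent for participation in the trial until the end-of-trial visit" (protocol 7.2.13). For a woman who attends her visits, "the end-of-trial assessments should take place at the last scheduled trial visit" (protocol 6.8). Because of the antibody samples, "the end-of-trial assessments can at the earliest be performed 21-28 days after the last MENOPUR liquid or MENOPUR powder dose" (same section). Which visit is her last depends on pregnancy:

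- Negative βhCG: she goes directly to end-of-trial (protocol 6.5.1).
- Positive βhCG, no vital pregnancy: end-of-trial follows the visit 5-6 weeks after transfer (protocol 6.6).
- Vital pregnancy: "If a vital pregnancy has been documented, the subject must attend a visit 8-9 weeks after transfer" (protocol 6.7).

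Protocol 9.8.2 words the definition differently. There the event must arise during treatment or worsen against the pre-treatment state, and end-of-trial is not named as a limit. SAP section 13 lists one departure from the protocol's analysis, the handling of center, and does not mention this one.

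**The concern.** The length of observation for adverse events is set by an outcome that the trial also evaluates. An arm with more pregnancies is watched longer on average and collects more events even if the formulation causes none. An arm with fewer pregnancies looks safer. Women who conceive also attend extra visits, and the adverse event question is asked at each one (protocol 8.2.1). Some reportable events, such as the pregnancy losses in protocol 8.4.4, can occur only after conception. The tables with 2% and 5% cut-offs and the adverse drug reaction tables use the same window.

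At stake is a stated secondary objective, the safety profile of the new formulation beside the old one. The primary non-inferiority inference is not touched.

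**Working it through.** The documents state no follow-up ratio, so there is no planned figure to reproduce. The check is arithmetic on the visit schedule.

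**Inputs, in days after the last IMP dose**

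- End-of-stimulation is the day of trigger (protocol 3.1.2). Retrieval is 36±2 hours after hCG and transfer is 5 days after retrieval (protocol 6.3). Counting retrieval as about 2 days after the last dose, transfer is at about 2 + 5 = 7.
- βhCG-negative: end-of-trial at 21-28, mid-point 24.5 (protocol 6.8).
- βhCG-positive, no vital pregnancy: 7 + 35 to 7 + 42 = 42-49, mid-point 45.5 (protocol 6.6).
- Vital pregnancy: 7 + 56 to 7 + 63 = 63-70, mid-point 66.5 (protocol 6.7).

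**Ratios after the last dose**

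- Vital pregnancy against βhCG-negative: 66.5/24.5 = 2.71. Extremes are 63/28 = 2.25 and 70/21 = 3.33.
- βhCG-positive without vital pregnancy against βhCG-negative: 45.5/24.5 = 1.86.

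**Ratios over the actual window, which starts at the first dose**

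- 10 stimulation days (assumed): (66.5 + 10)/(24.5 + 10) = 76.5/34.5 = 2.22.
- 20 stimulation days (the protocol maximum): 86.5/44.5 = 1.94.

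**Mean observation per arm** (10 stimulation days, two groups only, pregnancy rates assumed)

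- 40%: 0.40 × 76.5 + 0.60 × 34.5 = 51.3 days.
- 30%: 0.30 × 76.5 + 0.70 × 34.5 = 47.1 days.
- Ratio 51.3/47.1 = 1.09, a difference of about 9%.
- 35% against 30%: 49.2/47.1 = 1.045, about 4.5%.

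**Effect on the percentage of women with an event.** Let h be a constant weekly hazard of a first event (assumed) and T the window in days. The percentage is 1 − exp(−h × T/7), with T = 34.5 or 76.5.

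| h per week | Not pregnant | Vital pregnancy | Shift per 10-point pregnancy gap |
|---|---|---|---|
| 2% | 9.4% | 19.6% | 1.0 points |
| 5% | 21.8% | 42.1% | 2.0 points |
| 10% | 38.9% | 66.5% | 2.8 points |

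**How large a gap chance can produce.** With 200 per arm and an assumed 30% rate in both arms, the standard error of the difference is √(2 × 0.30 × 0.70/200) = 0.046. A gap of 5 points or more in either direction (z = 0.05/0.0458 = 1.09) occurs in roughly 28% of trials. A gap of 10 points or more (z = 2.18) occurs in about 3%. A 5-point gap carries half the shift in the table, about 0.5 to 1.4 points.

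**Choice of a common cut-off.** End-of-trial is allowed from day 21. With a cut at day 28, a woman who leaves at day 21 is still compared with women watched to day 28. The post-dose ratio is then up to 28/21 = 1.33, or 28/24.5 = 1.14 at the mid-point. With a cut at day 21, planned post-dose observation is 21 days for all, a ratio of 1.0.

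**The case against.** The other side has several fair points.

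- The adverse event tables are descriptive (protocol 9.8.1), so no between-arm test is distorted. This stands, and it limits the weight of the point.
- With equal pregnancy rates there is no differential effect. Both products contain the same drug substance, so no systematic difference is expected. This also stands. A chance imbalance remains possible.
- If the formulation did change pregnancy rates, the resulting events would be a real consequence of allocation, and counting them to end-of-trial is legitimate. That is a reason to keep those tables, but not to have only those.
- Several outcomes linked to pregnancy or timing already have suitable displays. Early pregnancy loss uses βhCG-positive women as denominator (SAP 10.2.3), OHSS is split into early and late (SAP 10.2.2), and injection site reactions are confined to stimulation (SAP 10.2.4). The general SOC/PT tables have no such treatment.

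A reader might infer that women with a pregnancy are observed 2.7 times as long over the whole treatment-emergent window. That ratio counts only the days after the last dose, whereas the SAP window opens at the first. A reader might also infer that the percentages must rise materially with pregnancy. Longer observation cannot lower them, but each woman is counted once per SOC and preferred term (protocol 9.8.2), and the rise depends on late event rates that the documents do not give.

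**Conclusion.** The dependence is real. End-of-trial, and with it the treatment-emergent window, comes later for women who conceive, and no planned table corrects for it. The size is modest: 1.9 to 2.2 times the observation over the full window for a vital pregnancy, and about 1 to 3 points in an arm's adverse event percentage for a 10-point pregnancy gap. These figures rest on transfer about 7 days after the last dose, window mid-points, 10 stimulation days (20 for the lower ratio), and assumed pregnancy rates and constant hazards.

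The documents do not support saying that the safety comparison is biased as planned. Between-arm distortion needs a difference in pregnancy rates, which is not known. With equal rates both arms move together, and only the absolute percentages are affected, including their position against the 2% and 5% cut-offs. This is a worthwhile, inexpensive improvement to the safety tables rather than a flaw in the trial's main conclusion.

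**What to change.** In SAP 10.2.1.1 and 10.2.1.2, add overview and SOC/PT tables restricted to events with onset from the first IMP dose to 21 days after the last IMP dose, and name these as the tables for the between-formulation comparison. Day 21 is the longest cut that lies within the planned follow-up of all treated subjects who do not withdraw early. The window still varies with the length of stimulation, but its end no longer depends on pregnancy. Keep the to-end-of-trial tables as the complete record.

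Reconcile the treatment-emergent definition in SAP 10.2.1 with protocol 9.8.2. If the SAP wording is kept, list the change in SAP section 13.

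The cost is one date cut and one extra set of tables. No new data are needed, because onset date and time are already recorded (protocol 7.2.13). The downside is that events after day 21 appear only in the complete-record tables.

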10.2.1.1 Overview of Treatment Emergent Adverse Events

A summary table for treatment-emergent adverse events will be presented, including for each treatment, the number of subjects reporting an adverse event, the percentage of subjects (%) with an adverse event, and the number of events (E) reported, for the following categories:

- Treatment-emergent adverse events.
- Treatment-emergent severe adverse events.
- Treatment-emergent non-serious adverse events.
- Treatment-emergent serious adverse events.
- Treatment-emergent adverse drug reactions.
- Treatment-emergent adverse events leading to discontinuation.
- Treatment-emergent deaths.

10.2.1.2 Incidence of Adverse Events

Treatment-emergent adverse events in each treatment group will be tabulated by system organ class (SOC) and preferred term (PT). The following will be presented: number of subjects reporting an adverse event, the percentage of subjects (%) with an adverse event, and the number of events (E) reported. AEs will be presented by SOC sorted alphabetically and PT sorted in decreasing frequency of occurrence.

Summary tables will be prepared for:

- All treatment-emergent adverse events.
- Treatment-emergent adverse events occurring in ≥2% and ≥5% of subjects in any treatment group.
- Treatment-emergent adverse drug reactions occurring in ≥2% and ≥5% of subjects in any treatment group.
- Treatment-emergent adverse events by causality.
- Treatment-emergent adverse events by intensity.
- Treatment-emergent adverse drug reactions by intensity.
- Treatment-emergent adverse events leading to discontinuation.

- Treatment-emergent serious adverse events.
- Treatment-emergent adverse events leading to death.

Supporting data listings will be provided for:

- All pre-NIMP adverse events sorted by SOC and PT.
- All pre-treatment adverse events sorted by SOC and PT.
- All treatment-emergent adverse events sorted by SOC and PT.
- All treatment-emergent adverse events sorted by center and subject number.
- All unique verbatim and coded terms.
- All SAEs.
- All non-Serious adverse events.
- All adverse events leading to discontinuation.
- All adverse events leading to death.

10.2.2 OHSS

OHSS for each treatment group will be tabulated by classification (mild, moderate, severe) and grade (1, 2, 3, 4, 5). These tabulations will be made for OHSS overall as well as separately for early OHSS and late OHSS.

10.2.3 Early Pregnancy Loss

Early pregnancy loss is defined as a positive β hCG test but no ongoing pregnancy at 8-9 weeks after blastocyst transfer. The early pregnancy loss rate will be presented by treatment group. The denominator for the early pregnancy loss rate consists of those subjects with a positive β hCG.

10.2.4 Injection Site Reactions

For each injection site reaction (redness, pain, itching, swelling, and bruising), the number of events and the number of subjects experiencing those events will be tabulated by time (immediately, 30 minutes, and 24 hours), reaction type, and intensity (none, mild, moderate, and severe). Because of the double-dummy design, injection site reactions for IMP (MENOPUR liquid and MENOPUR powder) will be summarized together and injection site reactions for Placebo (Placebo to MENOPUR liquid and Placebo to MENOPUR powder) will be summarized together.

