2 TRIAL OBJECTIVES AND ENDPOINTS

2.1 Objectives

Primary Objective

 To demonstrate non-inferiority of MENOPUR liquid versus MENOPUR powder with respect to the number of fertilized oocytes in women undergoing controlled ovarian stimulation.

Secondary Objectives

- To evaluate the pregnancy rates after stimulation with MENOPUR liquid and MENOPUR powder.
- To evaluate the follicular development during stimulation with MENOPUR liquid and MENOPUR powder.
- To evaluate the serum endocrine profile during stimulation with MENOPUR liquid and MENOPUR powder.
- To evaluate the number of oocytes retrieved, the number and quality of embryos, and the number and quality of blastocysts, associated with MENOPUR liquid and MENOPUR powder.
- To evaluate treatment efficiency of MENOPUR liquid and MENOPUR powder.
- To evaluate the safety profile of MENOPUR liquid and MENOPUR powder, including adverse events, routine safety laboratory parameters, local tolerability and immunogenicity.

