7.2.14 Injection Site Reactions

Every day throughout the stimulation period, the subjects will assess the local tolerability of subcutaneous injections of MENOPUR liquid or MENOPUR powder at three time points relative to the daily administration: immediately after the injection, 30 minutes after the injection and 24 hours after the injection. The subject will be informed to always inject MENOPUR liquid or Placebo to MENOPUR liquid using the pre-filled injection pen on the same side of the navel and MENOPUR powder or Placebo to MENOPUR powder using the syringe on the other side in order to be able to distinguish between injection site reactions related to MENOPUR liquid / Placebo to MENOPUR liquid and those related to MENOPUR powder / Placebo to MENOPUR powder. The following injection site reactions will be assessed: redness, pain, itching, swelling and bruising. The presence and intensity of each injection site reaction will be rated as one of the following: none, mild, moderate or severe.

The subject will record the assessments in a diary and the diary data will subsequently be transcribed to the e-CRF.

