8.4 Other Events of Special Interest

8.4.1 Injection Site Reactions

Injection site reactions after administration of IMP (MENOPUR liquid including Placebo to MENOPUR powder and MENOPUR powder including Placebo to MENOPUR liquid) are only to be reported as adverse events if they require active management, i.e. discontinuation of IMP, additional investigations or treatment of the injection site reaction. Local tolerability of IMP constitutes a secondary endpoint and will be evaluated in detail based on the subjects' recordings in the diary.

Local tolerability reactions after administration of NIMP are to be reported as adverse events if they fulfil the definition of an adverse event.

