9.8 Safety

9.8.1 General Considerations

Analyses for the safety analysis set will be conducted according to the actual treatment received.

Missing values will be treated as missing, except for causality, intensity, seriousness, and outcome of adverse events. A worst-case approach will be used: if causality is missing, the adverse event will be regarded as related to the IMP; if the intensity of an adverse event is missing, the adverse event will be regarded as severe; if seriousness is missing, the adverse event will be regarded as serious; if outcome is missing, and no date of outcome is present, the outcome is regarded as 'ongoing'.

Data will be presented by summary tables and listings only. Categorical data will be summarized by treatment using the number and percentage of subjects in each category. For calculation of percentages, the denominator will be the total number of subjects in the respective treatment group in the safety analysis set. Continuous data will be summarized by treatment using number, mean, standard deviation, median, minimum, and maximum.

All individual subject data will be listed per subject and treatment as observed including any derived values.

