11.3 Neonatal Health

The gestational age, gender, weight, length, and Apgar scores (1 minute, 5 minutes, and 10 minutes) will be presented by treatment group. Furthermore, admissions to care units (NICU, NCU, or PCU), admissions to care units for longer than 2 hours, malformations or congenital anomalies, neonatal death, and important medical events will be presented by treatment group at birth, at 4 weeks after live birth, and after 6 months following live birth.

Neonatal SAEs will be summarized from birth through a minimum of 6 months after birth. Written narratives will be issued for all SAEs.

Parameters relating to maternal health will also be presented by treatment group. These will include clinically relevant pregnancy, labor, or delivery complications, COVID-19 infection, exposure to risk factors of congenital anomalies or malformations, and maternal death in connection with pregnancy or labor.

12 Interim analyses

A sample size reassessment will be performed without breaking the blind and without meaningful inflation of the Type I error of the trial (see Appendix 1), in line with the current regulatory guidelines for non-inferiority trials by the Food and Drug Administration (FDA). The one-sample standard deviation of the primary efficacy endpoint will be evaluated in a blinded manner in relation to the assumptions underlying the sample size calculation.

The sample size reassessment is to take place when 70% of the planned sample size has provided a primary endpoint (280 primary endpoints) or when 300 subjects have been randomized, whichever occurs first.

A restricted recalculation rule for the sample size reassessment will be used. The trial will originally target 400 randomized subjects. At the time of the interim analysis, the estimated one-sample standard deviation will be used to recalculate the required sample size. If the recalculated sample size is less than 400, then the targeted sample size will remain at 400 (i.e.; the sample size will never decrease below 400). If the recalculated sample size is greater than 400, however, then the targeted sample size will be increased to either the recalculated sample size or 500, whichever is smaller.

13 Deviations from the protocol

There is one deviation from the planned analysis in the protocol. Center will be incorporated into statistical analyses as a fixed effect instead of a random effect.

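### SAP Section 10.2.4, as written, merges injection site reactions to liquid and powder, contrary to the protocol's by-treatment rule for safety tables and without being declared as a deviation

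*SAP*

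**What the plan says.** SAP Section 10.2.4 tabulates events and subjects for each reaction (redness, pain, itching, swelling, bruising) by time, reaction type and intensity. It then cites the double-dummy design as the reason for two instructions. The first is that "injection site reactions for IMP (MENOPUR liquid and MENOPUR powder) will be summarized together". The second treats the two placebos in the same way, with a single summary for both. Treatment group is not mentioned.

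The protocol's general safety rule (Section 9.8.1) is: "Categorical data will be summarized by treatment using the number and percentage of subjects in each category". The denominator is the size of the respective treatment group in the safety analysis set. Protocol Section 9.8.4, on injection site reactions, lists time, reaction and intensity and makes no exception to that rule.

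Protocol Section 7.2.14 has the pen and the syringe used on opposite sides of the navel "in order to be able to distinguish between injection site reactions related to MENOPUR liquid" or its placebo from those related to the powder or its placebo.

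SAP Section 13 states: "There is one deviation from the planned analysis in the protocol". That deviation is the handling of center as a fixed effect.

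**The concern.** Followed word for word, Section 10.2.4 gives one summary for all active injections and one for all placebo injections. Neither can show whether the new liquid is tolerated better or worse than the powder, although the trial was set up to describe exactly that. The secondary safety objective reads: "To evaluate the safety profile of MENOPUR liquid and MENOPUR powder, including adverse events, routine safety laboratory parameters, local tolerability and immunogenicity". The frequency and intensity of injection site reactions is also a listed secondary endpoint.

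No other table fills the gap. Under protocol Section 8.4.1, injection site reactions to the trial products "are only to be reported as adverse events if they require active management", so most diary entries never reach the adverse event tables. On the literal reading, a difference between formulations would be visible only in subject listings.

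**Working it through.** This is mainly a comparison of texts. The plan states no figure on this point that could be reproduced.

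**Step 1: does the wording conflict with the protocol?**

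| Source | Rule |
|---|---|
| Protocol 9.8.1 | Categorical safety data by treatment; denominator is the treatment group |
| Protocol 9.8.4 | Time, reaction, intensity; no exception to 9.8.1 |
| SAP 10.2.4 | Time, reaction type, intensity; the two actives together, the two placebos together |
| SAP 13 | One deviation, center as a fixed effect |

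A merged column does not satisfy 9.8.1. It also cannot use the 9.8.1 denominator, because it spans both treatment groups. The SAP version 2.0 change history does not mention injection site reactions.

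**Step 2: does another part of the SAP settle the reading?**

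- SAP 10.1 sends the reader to SAP 1.2.1, which specifies the statistics to present but sets no by-treatment default.
- SAP 10.1 also says: "All individual subject data will be listed per subject and treatment as observed including any derived values". That governs listings, not summary tables.
- SAP 14 places tables, listings and figures in a separate document, which is not part of the material available here.
- SAP 10.2.4 uses IMP for the active products only. SAP 4 and 6.2 use it for the active product including its accompanying placebo. The term therefore does not help.

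**Step 3: what would a merged table hide?**

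Inputs: 200 subjects per arm (protocol Section 3.2). Reaction rates are assumed, because the documents give none. Let pL and pP be the proportions of subjects with a given reaction to the liquid and to the powder.

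Merged proportion = (200 × pL + 200 × pP) / 400 = (pL + pP) / 2

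| pL | pP | Merged | Difference by arm |
|---|---|---|---|
| 55% | 45% | (110 + 90)/400 = 50% | 10 points |
| 60% | 40% | (120 + 80)/400 = 50% | 20 points |
| 70% | 30% | (140 + 60)/400 = 50% | 40 points |
| 20% | 20% | (40 + 40)/400 = 20% | 0 points |
| 10% | 30% | (20 + 60)/400 = 20% | −20 points |
| 0% | 40% | (0 + 80)/400 = 20% | −40 points |

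The pairs were chosen to share an average. The general point is that, with equal arms, the merged figure depends only on the sum of the two rates and carries no information on their difference. The literal reading gives 2 columns of N = 400. The by-arm reading gives 4 columns of N = 200.

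**The case against.** The best defense is that the authors never meant to merge the arms. In a double-dummy trial each subject gives herself one active and one placebo injection a day. That is a good reason to keep active-injection reactions apart from placebo-injection reactions, and no reason to combine liquid with powder. On this view, summarizing together means one display for actives and one for placebos, each with a column per arm. Three further points support it:

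- Where the SAP means merging, as with small centers in Section 9.1.2, it speaks of pooling.
- The missing reference to treatment group follows the wording of protocol Section 9.8.4. SAP Sections 10.2.6, 10.2.7.1–10.2.7.3, 10.2.8, 10.2.9 and 10.2.10.1–10.2.10.3 omit it too, and nobody would read those as merging the arms.
- Declaring a single deviation suggests that no departure was intended here.

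This makes the by-arm reading plausible, and if it was intended nothing is lost but clarity. It does not remove the problem. The other sections are merely silent, whereas this one adds an instruction to put the two products together. Nothing in the SAP text says which reading is meant, and a programmer could reasonably produce either table. The table shells may resolve it, but the SAP should not depend on them for a named secondary endpoint.

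It is also true that the harm is limited. The diary keeps the two injection sides apart, the listings are by subject and treatment, and the summary is descriptive.

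**Conclusion.** The concern holds in its qualified form. Read literally, SAP Section 10.2.4 merges the two formulations, conflicts with protocol Section 9.8.1, and is not declared in SAP Section 13. A compliant reading exists, but the SAP does not establish it.

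On the literal reading, the only planned summary of local tolerability cannot show any difference between liquid and powder, whatever its size. The 10, 20 and 40 point gaps shown above rest on assumed rates and the planned 200 per arm, and say nothing about what this trial will find. On the by-arm reading the defect is one of wording only. The primary analysis, the error rates and the collected data are unaffected under either reading. Confidence is medium, because the intended layout cannot be confirmed from the protocol and SAP alone.

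**What to change.** Replace the last sentence of SAP Section 10.2.4 with wording such as:

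> Reactions to active injections and reactions to placebo injections will each be tabulated by treatment group, in four separate columns: in the liquid arm, MENOPUR liquid (pen) and Placebo to MENOPUR powder (syringe); in the powder arm, MENOPUR powder (syringe) and Placebo to MENOPUR liquid (pen). Each column is broken down by reaction, time and intensity. Percentages use the number of subjects in that treatment group of the safety analysis set.

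The table remains descriptive, as protocol Section 9.8.1 plans, and no inferential comparison is needed. Because this wording follows the protocol, it requires no further entry in SAP Section 13. The cost is one sentence and a table shell. No new data are needed, since pen and syringe reactions are already kept apart by side of the navel and recorded in the diary.
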